Appendix 4: AbiliTech Medical APEX Device Feedback Questions

[name]
[contact] www.abilitechmedical.com

AbiliTech Medical APEX Device Subject Device Survey Questions

APEX Survey Monkey Questions

[figure not shown]

1. What is your gender?
 											

2. What is your age?
 
 18-29 years old
 
 30-49 years old
 
 50-64 years old
 
 65 years and over
											

3. How long ago was your injury?
 

 less than 6 months	 5- 10 years ago	

 6 months to 1 year ago	 10-20 years ago	

 1 - 2 years ago	 25+ years ago	

 2 - 5 years ago		

		 less than 6 months	 5- 10 years ago	 6 months to 1 year ago	 10-20 years ago	 1 - 2 years ago	 25+ years ago	 2 - 5 years ago			
 less than 6 months	 5- 10 years ago										
 6 months to 1 year ago	 10-20 years ago										
 1 - 2 years ago	 25+ years ago										
 2 - 5 years ago											

4. How were you injured?
 

 Sports (any type including diving, surfing, ...)	 Non-Traumatic Cause (birth, infected, tumor, ...)	

 Transporting (car, truck, ATV, motorcycle, bike, ...)	 Other Traumatic Cause	

 Slip, Trip, or Fall (including falls from height)	 Unknown	

 Assault (stab, gunshot, ...)		

 Other (please specify)		

		 Sports (any type including diving, surfing, ...)	 Non-Traumatic Cause (birth, infected, tumor, ...)	 Transporting (car, truck, ATV, motorcycle, bike, ...)	 Other Traumatic Cause	 Slip, Trip, or Fall (including falls from height)	 Unknown	 Assault (stab, gunshot, ...)		 Other (please specify)	
 Sports (any type including diving, surfing, ...)	 Non-Traumatic Cause (birth, infected, tumor, ...)										
 Transporting (car, truck, ATV, motorcycle, bike, ...)	 Other Traumatic Cause										
 Slip, Trip, or Fall (including falls from height)	 Unknown										
 Assault (stab, gunshot, ...)											
 Other (please specify)											

5. My injury is defined as:
 

 ASIAA: No Motor & Sensory	 ASIAD & E: Functional Motor Skills Below Injury	

 ASIA B: No Motor & Some Sensory	 Unsure	

 ASIA C: Significant Motor & Some Sensory		

		 ASIAA: No Motor & Sensory	 ASIAD & E: Functional Motor Skills Below Injury	 ASIA B: No Motor & Some Sensory	 Unsure	 ASIA C: Significant Motor & Some Sensory					
 ASIAA: No Motor & Sensory	 ASIAD & E: Functional Motor Skills Below Injury										
 ASIA B: No Motor & Some Sensory	 Unsure										
 ASIA C: Significant Motor & Some Sensory											

6. What level is your injury?

[figure not shown]
- C1
- C2
- C3
- C4
- C5
- C6
- C7
- C8

Other (please specify)

7. I have full functional strength in my arms

8. I have fully functional hand grip

9. Assuming your limited function, please list the top three things you would want to do with a shoulder, elbow, hand movement device.

10. I use a...

- Power Wheelchair
- Manual Wheelchair
- Cane/ Walker
- No Assistance Required
- Please list Device Manufacturer:

11. If you are unable to do so, how important is the ability to independently...

	Very Important	Important	Neutral/ Undecided	Unimportant	Very Unimportant	N/A, Functional
Actively move your arm(s)? (Shoulder & Elbow)						
Open your hand?						
Close your hand?						
Twist your palm? (Pronate and Supinate)						
Move your wrist?						
Improve pinch or grasp strength in your hand?						
Pick up everyday objects? (Pen, fork, food, soda can, folder/notebook)						
Perform Activities of Daily Living? (Brushing teeth, eating, drinking, grooming, ...)						
Other (please specify)						

12. Which statement best describes your current living arrangement?

- I live independently
- I live with my family
- I live in a post-acute care facility
- I live in a long term care facility
- Other (please specify)

13. What are the top five things you would like the device to help you accomplish that you can not do?

	1st	2nd	3rd	4th	5th	N/A
Grooming						
Dressing						
Self-catherize						
Perform my own bowel program						
Wheeling						
Transferring						
Cleaning						
Food preparation						
Desk/Computer Work						
Eating and Drinking Independently						
Scratch an itch						
Shake hands						
Wave						
Hug a loved one						
Cell Phone						
Driving						
Manage my power chair independently						
Other (please specify)						

14. For which activities of daily living are currently receiving help from a caregiver? (Check all that apply)

- Grooming
- Dressing
- Self-catheterize
- Performing my bowel program
- Wheeling
- Transferring
- Cleaning
- Food preparation
- Desk/Computer Work
- Eating and Drinking Independently
- Scratch an itch
- Shake hands
- Wave
- Hug a loved one
- Cell Phone
- Driving
- Manage my power chair independently
- Other (please specify)

15. What forms of transportation do you use? (Check all that apply)

- I own an accessible car/van
- I rely upon a caregiver for transportation
- I use metro mobility or similar transportation
- Public Transit
- Taxi
- Other (please specify)

16. I have seen the following specialists within the last (blank) years:

	1 year	3 years	5 years	Over 5 years	N/A
General Practice Physician					
Physical Medical Rehabilitation Physician					
Neurologist					
Occupational Therapist					
Physical Therapist					
Respiratory Therapist					
Orthotist/Wheelchair Fitting Expert					
Orthopedic Pain Management Specialist					
Cardiologist					
Urologist					

Other (please specify)

17. My SCI doctor is at (blank hospital):

18. How many times do you visit a doctor or medical professionals in a one year period?

19. I experience pain:

- Daily
- Weekly
- Monthly
- I do not experience pain
- Other (please specify)

20. Rate your average pain. (0 is none, 10 is worst possible pain)

21. Where is your pain located?

22. I have spasticity:

23. I take medicine for spasticity:

24. I have shoulder subluxation:

25. Do you practice in-home therapy or fitness?

If yes, how often?

26. Do you participate in therapy outside of the home?

If yes, how often?

27. What type of insurance do you have? (Check all that apply)

- Private
- Medicaid
- Employer
- Disability
- None

28. Do you currently pay for a caregiver?

- Yes, Private Pay
- Yes, Insurance/ Government Assistance
- No

29. What kind of home care do you have? (Check all that apply)

- Nurse
- Personal Care Assistant
- House Keeper/ Cleaner
- None
- Other (please specify)

30. How much do you pay your care giver per hour?

31. How many hours per day do you require a paid caregiver?

How many hours are you approved for?

32. Does a family member provide care?

If yes, how many hours per day of care is done by a family member?

33. Do you track your yearly healthcare costs?

If yes, what is your annual cost?

34. Does your injury impact any family members ability to work?

- Yes
- No

35. Does your arm/hand function impact your ability to work in your field of choice?

- Yes
- No
- Other (please specify)

36. Are you currently employed?

- Yes
- No

37. Would you work if you could use your arms/hands?

- Yes, Part Time
- Yes, Full time
- No
- Other (please specify)

38. Would you go to school if you could use your arms/hands?

- Yes, Part Time
- Yes, Full time
- No
- Other (please specify)

39. Please select and rank your satisfaction on a scale of 1 (low) - 10 (high) with the assistive devices you have used for upper limb impairment treatment

	1	2	3	4	5	6	7	8	9	10	N/A Never Used
Basic Splint											
Tenodesis Splint											
Bioness											
Myopro											
Hacoma/Armeo Spring											

Other (please specify)

40. Do you use any assistive devices for arm/hand function? What do you like about them?

41. What limitations have you found with other assistive devices for arm/hand function?

42. Please react to the following statements on assistive device features.

	Yes	Maybe	No	N/A
If I could use my arms, I'd be willing to use accessories to compensate for a loss of hand function				
A three finger grip would meet my requirements				
A five finger grip would meet my requirements				
I would be interested in seeing a weekly progress report of my activity with my arms, similar to a fitbit				
A device would need to show my daily or weekly activity progress on a smartphone				

43. Would you be interested in...

	Yes	Maybe	No
Using an app to see with your phone to see how much you have used your exoskeleton?			
Using an app that shows you how you have built strength or function?			
Using an app that connected with your clinician to show them your usage and progress with the device?			
Using an app to see daily reports?			
Using an app to see weekly reports?			
Using an app to see monthly reports?			

44. To control an upper limb prosthesis I would like to use:

	Very Interested	Interested	Maybe	Uninterested	Very Uninterested
Button/ Switch					
Body/ Head Activated Movement					
Voice Control					
Eye Tracking					
Mouth/Bite Click					
Sip n Puff					
EMG (Trace but detectable muscle movement)					
Pressure Sensors					
Other (please specify)					

45. How important is:

	Very Important	Important	Neutral	Unimportant	Very Unimportant	N/A
Wrist Support						
Wrist assisted movement with finger assisted movement						
Stabilize the wrist during hand and finger motion						
Individual finger movement (i.e.: just move index or middle finger at a time)						
Lightweight (under 2 lbs)						
Mid weight (2-4 lbs)						
4-6lbs						
Fashionable/ Style						
Durability						

Other (please specify)

46. What other interventions have you done to work on improving your hand/arm function?

47. It is important to me to have use of both of my arms:

- Yes, I need assistance for both arms
- No, I need assistance for a single arm
- Other (please specify)

48. Is there a caregiver available to assist with putting on a hand based device?

- Yes
- No

49. If you play video or computer games, my top three favorites are:

50. Which of the following is most important to me about how the device looks? (Check all that apply)

- Color
- Shape
- Size
- Texture

51. I would use this device for X hours a day

- 1-2 hours
- 2-4 hours
- 4-6 hours
- 6+ hours

52. If this device were useful to me and insurance would not cover it, the maximum amount I would pay for a hand grip device would be...

- \$1,000
- \$10,000
- \$2,500
- I would not pay for this
- \$5,000

53. How long should the battery last until it needs to be recharged?

- 4 hours
- 8 hours
- 24 hours
- 48 hours

54. Other than lack of voluntary movement, do you have any limitations that would prevent finger or hand movement?

55. Do you have any safety concerns for this device?

56. If safety concerns, please comment.

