1.4. Study Rationale

Currently there are no effective mobile devices that enable people with limited upper extremity movement to move their upper extremities, especially for individuals with upper level SCI (C1-5). This

severely limits independence, reduces the ability for individuals with this condition to complete ADL's and makes them dependent on caregivers to complete all physical interactions with their environment. We hypothesize that the APEX device can safely enable and control shoulder-elbow movement to improve ADL performance and independence. Individuals with upper level cervical spinal cord injury that have lost functional use of their arms have a high potential to increase their quality of life by using this device which justifies observing their interaction with the APEX Focus Group.

2. Objectives

Objectives:

Perform focus groups with subjects and clinicians to evaluate a proof of concept active powered prosthesis.

1. Perform a focus group with three to six individuals with chronic tetraplegia to evaluate the user control interface of an active powered prosthesis device proof-of-concept prototype. Subjects will provide feedback on the device function and usability after manipulating the device on a mannequin.
2. Perform a focus group with Courage Kenny Research Institute Clinicians to validate device safety features, performance and assess the potential clinical utility of the device.

Primary Outcomes:

The following will be assessed:

1. User ability to control APEX device to manipulate objects in space
2. User ability to control APEX to move an object in a preferred pathway
3. User ability to control APEX device to push buttons
4. User ability to control APEX to lift a phone
5. Evaluate subject reported outcomes within their interaction with the APEX device through interviews and a survey

Secondary Outcomes:

1. To observe and assess any uncontrolled device guided movement during the APEX device testing on mannequin
2. Gain clinician feedback on device safety control mechanisms

Ancillary Data:

1. Subject Acclimatization/ Learning Time to Operate the APEX Device.
2. Characterization of focus group population
 - a. Medical History: Diagnosis, level of injury, AIS classification
 - b. Subject examination: MMT scores
3. Feedback on device design
4. Feedback on user input control system

3. Trial Population

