Target user population will be three to six individuals with spinal cord injury at levels C3 to C5, and AIS A, B, or C. Inclusion and exclusion criteria are below:

3.1 Inclusion Criteria:

1. Spinal cord injury at levels C3 to C5, and AIS A, B, or C
2. Greater than 3-months post injury or surgery to spinal column, arms, or shoulder
3. Ability to provide informed consent
4. Age 18 or over
5. Selected for participation based on investigator discretion

3.2 Exclusion Criteria:

1. Unable to follow instructions
2. Exhibit significant behavioral problems or impaired cognitive ability
3. Inability to provide consent
4. Non-English speaker

Clinicians involved in overseeing the device manipulation portion of the study will be expected to provide feedback about the APEX device.

4. Study Design

Part 1: The study design will be that of a single-arm pilot study with three to six human subjects (n=3-6). The study will inform the AMI design team of customer and APEX design requirements needed to develop an APEX device for commercial release. Participants will be expected to attend one 180 minute session. AbiliTech Medical personnel will be present for user training, during all device evaluation sessions and to troubleshoot technical problems. Courage Kenny Rehabilitation Institute (CKRI) personnel will collect subject medical history from medical records once consent and HIPAA authorization are obtained. Appendix 1, section 1 includes subject information to be collected. Potential participants will receive the consent form ahead of time to read and study. At the start of visit 1, subjects will be consented as a group and sign the HIPPA authorization. During device testing, Appendix 2 and 3 include assessment forms for device testing and questions subjects will be asked. Appendix 4, includes the device feedback survey which will be completed onsite before conclusion of the study. Subjects will use their personal internet connected mobile device to access and complete the survey. If subjects do not have a mobile device, a tablet will be available for subject to use and complete the survey. Audio recordings will be taken and videos of the mannequin will be recorded during device movement. Table 1 highlights activities to be performed in the User Focus Group.

Table 1: Visit 1: User Focus Group Activities

	Activity	Description

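### Survey item 47 joins the importance of using both arms to the number of arms needing help, so its answer is ambiguous as a one-arm or two-arm device requirement

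*Combined protocol and SAP*

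**What the plan says.** Appendix 4 holds the 56-item survey that subjects complete onsite at Visit 1. Item 47 reads "It is important to me to have use of both of my arms" and offers three answers: "Yes, I need assistance for both arms", "No, I need assistance for a single arm", and a free-text Other.

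The people answering are described in section 3 as having "spinal cord injury at levels C3 to C5, and AIS A, B, or C". No criterion concerns arm function, or whether both arms are affected equally. Section 1.4 describes the intended users as "Individuals with upper level cervical spinal cord injury that have lost functional use of their arms".

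Two passages give the survey its weight. Section 2 lists, as the fifth primary outcome, "Evaluate subject reported outcomes within their interaction with the APEX device through interviews and a survey". Section 4 gives the purpose: "The study will inform the AMI design team of customer and APEX design requirements" for a commercial device. Section 8 states that no statistical analysis will be done, because only three to six subjects take part.

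**The concern.** The stem asks for a preference: does using both arms matter to you? The answers report a quantity: how many arms need assistance. A subject can hold any view on the first whatever the truth of the second, yet the fixed answers force them to move together.

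At stake is one design question. Section 1.2 describes APEX as a worn chassis carrying processing, power, motors and cables, so whether it must drive one arm or two is a basic requirement. Item 47 is the only place where the study comes near to asking. If a Yes may mean either that both arms are impaired or that a one-arm device would not do, the design team cannot tell which it has been told. With raw answers from a handful of subjects and no analysis, nothing done later can separate the two.

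**Working it through.** The plan gives no figure for this item, so there is none to reproduce. The check sets the wording beside the other instruments.

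**Step 1: what the fixed answers can express.** Take need (both arms or one) and importance of using both (yes or no). That gives 2 × 2 = 4 positions.

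| Need | Both arms important | Both arms not important |
|---|---|---|
| Both arms | fixed answer Yes | no fixed answer |
| One arm | no fixed answer | fixed answer No |

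Two of the four have a fixed answer. The other two are misrecorded or go to Other.

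**Step 2: what the answer means for one subject.** The words about needing assistance allow two readings: (A) the subject's present impairment; (B) the help wanted from a device.

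- Both arms impaired, content with one powered arm. Under A, the need half of the answer points to Yes. Under B, it points to No. The same person may tick either, and the reading used is not recorded.
- One arm impaired, both arms valued. Yes misstates the need and No misstates the importance. Neither reading removes the conflict.

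**Step 3: whether another item supplies the answer.**

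- Survey item 7 asks about strength in the arms together, and item 11 writes arm with an optional plural. Neither separates one from two.
- Survey items 9 and 13 collect and rank desired activities, not the number of arms.
- The open-ended utility and device questions that follow the usability form in Appendix 2 speak of the arms in the plural. They could bring the matter out but do not ask it.
- The muscle-test fields in Appendix 1 have no left and right.
- The clinician questions in Appendix 5 do not raise it.

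**Step 4: size.** The documents give neither the share of subjects with need in both arms nor the share who would read the item as A or B. As far as they go, each could lie anywhere from 0 to 100%. One subject is 1/6 = 17% of the largest planned group and 1/3 = 33% of the smallest. A single subject who moves from Yes to No by reading the item the other way therefore shifts the reported share by 17 to 33 percentage points. That shows how sensitive the tally is; it does not estimate the error.

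**The case against.** The strongest reply is that reading B is the natural one. Item 47 follows items on control method, weight and style and comes just before one on putting a device on. In that setting, needing assistance for a single arm plausibly means wanting a device for one arm, and the item then does bear on the question. This stands in part: the answer is ambiguous rather than unreadable. It does not clear the item, because nothing tells the subject which reading is meant.

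Next, the free-text Other is available. With three to six subjects answering onsite, each comment can be read, and Visit 1 includes a group discussion. This also stands. Its limit is that free text helps only a subject who notices the mismatch; one who simply ticks Yes leaves no trace of it.

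Third, no decision rule is tied to item 47, and section 6 judges feasibility on intentional control, usability feedback and clinician feedback. That is correct and keeps the matter small.

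A reader might go further and infer that at C3 to C5 a Yes is practically forced, so that the item will come back unanimous whatever subjects prefer. The documents do not support this. It requires that every subject needs help with both arms, that every subject reads the answers as impairment only, and that none uses Other. Eligibility sets no requirement for impairment in both arms and admits AIS C, and the description in section 1.4 carries no proportion.

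**Conclusion.** The point holds as a minor defect of survey wording. Item 47 ties importance to need, two of the four possible positions have only free text, and no other question asks directly about one arm or two. A Yes or No should not be reported as a design requirement without that caution.

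This rests on the printed wording alone and needs no assumption about how many subjects have both arms affected. That share is not given, so the size of any distortion cannot be stated. Nor do the documents say that the sponsor would take a Yes as demand for a two-arm device; that is a risk of misreading, not a stated plan. The mannequin tasks, the observation of uncontrolled movement and the protection of subjects are unaffected.

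**What to change.** Replace item 47 with two items.

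(a) *Which arm(s) do you currently need help to move?* Left / Right / Both / Neither.

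(b) *Would a device that powers only one arm be useful to you?* Yes, my dominant arm / Yes, my other arm / No, only a device powering both arms would be useful / Unsure / Other, with space to specify.

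Report (b) as the design-requirement answer and (a) as description of the subjects. Item (a) includes Neither because eligibility sets no threshold of arm function, and (b) keeps the free-text route that the present item offers. The answers to (b) speak only of usefulness, so need is not mixed in again.

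The cost is one extra survey question, plus the IRB submission that section 10 requires for any amendment. The change has to be made before the user session, because section 4 plans only one session per subject and section 5.3 allows no data afterwards except for a related adverse event.
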